Protocol Clinical Trial

Study synopsis

Study overview	
Title of clinical trial	Low grade inflammation in childhood obesity : an independent risk factor for endothelial dysfunction ?
Sponsor name	University Hospital of Brussels
Principal Investigator	prof. dr. [name] / [name]
Medical condition or disease under investigation	Obesity and overweight, cardiovascular risk factors
Purpose of clinical trial	To assess whether low grade inflammation in childhood obesity contributes to endothelial dysfunction
Primary objective	To investigate if the reactive hyperemia index by peripheral arterial tonometry is higher in adolescents with a history of childhood obesity and presenting a low grade inflammation in comparison with those without low grade inflammation (hSCRP < or > 1 mg/L)
Secondary objective (s)	To analyze the changes in hCRP and adiposity in obese children and adolescents after 5 to 10 years
Trial Design	Observational cohort study
Endpoints	RH-PAT scores, measured by peripheral artery tonometry . hSCRP, measured by automated immunoturbidometry BMI z-score and % body fat by skinfold thickness
Sample Size	54 (α= 0,05 – power 80%)
Summary of eligibility criteria	Overweight and obese adolescents, aged 12 to 21 years, with a known level of hs-CRP at initial evaluation for metabolic syndrome
Maximum duration of intervention	Single visit
Version and date of final protocol	Protocol version 1, date 18/08/2018
Version and date of protocol amendments	Not applicable

Study Schedule

Administrative information

1. Sponsor

The study is sponsored by the division of pediatric endocrinology of the University Hospital of Brussels (UZ Brussel).

2. (Principal) Investigator(s)

Prof. dr. [name]

Dr. [name]

[name]. [name]

[name] [name]

[name]

3. Departments involved

Department of Pediatrics

Division of Pediatric Endocrinology

University Hospital of Brussels

[name]

Ethical and regulatory information

1. Study registration

The study is registered at ClinicalTrials.gov and has a unique number: ####.

2. Study type

The study is an observational cohort study

3. Competent Ethics Committee

Central Ethics Committee:

Ethical Committee University Hospital of Brussels

[contact]

Email: [contact]

4. Ethical conduct of the study

The trial will be conducted in compliance with the principles of the Declaration of Helsinki (current version), the principles of Good Clinical Practice (GCP) and in accordance with all

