The statistical analysis will be done with the SPSS software.

The difference in THI index between the population with and without low grade inflammation will be evaluated by the Mann Whitney U test and Multivariate analysis of variance, taking current hCRP, age, BMI z-score, and systolic blood pressure into account. The change in hS

CRP in the population with and without low grade inflammation will be analyzed by the Kruskall Wallace test.

The power calculation was done at clincalc.com/stats/samplesize software. Assuming a mean RHI score of 1.51 in overweight children with a standard deviation of 0.2 (9), assuming an equal distribution between the study groups (elevated vs. normal hs-CRP), we have a power of 0.80 to demonstrate a difference of 20 % between the two groups with 27 patients enrolled in each group.

Study population

1. Recruitment

Eligible candidates will be recruited within the children with overweight and obesity having a metabolic risk evaluation before treatment in the period 2006 and 2010 at the pediatric clinic of the UZ Brussel. In total 60 participants will be investigated. Firstly, 30 participating patients with initially elevated hsCRP will be selected at random (following the date of their initial investigation) and afterwards matched for age, BMI z-score, and blood pressure with the same number of patients without initially elevated hCRP values

2. Recruitment procedure

Eligible candidates, or their parents if underage, will be personally contacted by telephone and/or e-mail by their initial pediatric endocrinologist and will be invited to partake in the study. All written information about the study will be provided beforehand.

3. Eligibility criteria

➤ Inclusion Criteria:

- Age 12-21 years at the moment of evaluation
- BMI > 1.3 SDS at the initial evaluation
- Hs-CRP available at initial evaluation

➤ Exclusion Criteria

- Acute or chronic Infection at the time of the study visit

Be or have been a smoker of tobacco

Study intervention

1. Study overview

A single visit is planned. During this visit a standard questionnaire on current health status, life style will be filled in a selfscore of pubertal development using standardized pictures will be done. Standard anthropometrics and blood-pressure measurements , a blooddrawn for hSCRP and a peripheral artery tonometry will be performed.

2. Identification of intervention

➤ Anthropometry:

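### Time since initial evaluation is neither matched nor modelled, and an unclear date-based selection rule could make it differ between the hs-CRP groups

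*Combined protocol and SAP*

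**What the plan says.** - **Source population** (Study population, 1. Recruitment): children with overweight or obesity "having a metabolic risk evaluation before treatment in the period 2006 and 2010".
- **Elevated group** (same section): the 30 patients with initially elevated hs-CRP "will be selected at random (following the date of their initial investigation").
- **Comparison group** (same section): "afterwards matched for age, BMI z-score, and blood pressure with the same number of patients without initially elevated hCRP values". The section does not say whether the matched age is age at the initial evaluation or at the study visit, or in what order controls are approached.
- **RHI analysis** (Study design, 3. Statistical methodology): an unadjusted Mann-Whitney test, and a multivariate analysis of variance "taking current hCRP, age, BMI z-score, and systolic blood pressure into account".
- **hs-CRP change analysis** (same section): a Kruskal-Wallis test between the groups, with no covariates.
- **Follow-up** (Study synopsis): the secondary objective is "To analyze the changes in hCRP and adiposity in obese children and adolescents after 5 to 10 years". The document is "Protocol version 1, date 18/08/2018", and each participant has one visit.

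**The concern.** A list worked through in date order is not a random sample of that list. If the order starts at one end of 2006-2010 and stops at 30 patients, the elevated group sits in one part of the window while controls may come from any year. Nothing in the matching would correct this. If age is matched at the initial evaluation, the groups then differ in age at the visit. If it is matched at the visit, they differ in age at the initial evaluation and in duration.

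Any change in hs-CRP or RHI that comes with elapsed time could then appear as an effect of low grade inflammation, or hide one. The hs-CRP change comparison is the most exposed, because change over time is its subject and its test has no adjustment. Selection and matching cannot be redone after enrolment.

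**Working it through.** **1. The plan's own interval.** The inputs are the 2006-2010 window (Recruitment) and the protocol date, 18 August 2018 (synopsis), taken as the earliest plausible visit.

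- From 1 January 2006: 12.63 years.
- From 31 December 2010: 7.63 years.
- Spread: 12.63 - 7.63 = 5.0 years.

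The synopsis interval of 5 to 10 years is not reproduced, since patients first seen before August 2008 exceed it.

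**2. Size of a possible gap.** The documents do not give the number M of available elevated patients, so it is varied. The assumptions are even entry over 5 years, elevated patients taken as the first 30 by date, controls spread over the whole window, and no effect of the age matching on dates.

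The mean entry time of the first 30 of M is 5 × 15.5/(M + 1) = 77.5/(M + 1) years, against 2.5 for controls. So the gap is 2.5 - 77.5/(M + 1):

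| M | Gap (years) |
|---|---|
| 30 | 2.5 - 2.50 = 0.0 |
| 40 | 2.5 - 1.89 = 0.6 |
| 60 | 2.5 - 1.27 = 1.2 |
| 90 | 2.5 - 0.85 = 1.6 |
| 120 | 2.5 - 0.64 = 1.9 |

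Simulation gives the same values to one decimal. Starting from the end of the window reverses the sign.

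**3. What a gap could do to RHI.** No slope of RHI per year is given, so 0.02 to 0.05 is assumed. The yardsticks are the plan's SD of 0.2 and its target difference, 20% of 1.51 = 0.302. Bias is slope × gap. The last column is the simulated rejection rate of a two-sided 5% Mann-Whitney test with 30 per group and no true group effect.

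| Gap (years) | Bias | Share of 0.302 | Rejection rate |
|---|---|---|---|
| 0 | 0 | 0% | about 5% |
| 0.6 | 0.012-0.030 | 4-10% | 5-8% |
| 1.25 | 0.025-0.062 | 8-21% | 7-19% |
| 2.0 | 0.040-0.100 | 13-33% | 11-45% |

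**4. How far the age term helps.** Suppose initial age is matched, current age is the model covariate, and RHI depends on duration. Current age is initial age plus duration, so the share of the duration bias that remains is

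var(initial age) / [var(initial age) + var(duration within group)].

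With elevated patients from the first one or two years (variance 1/12 or 4/12) and controls over five (25/12), the average within-group variance is 1.08 or 1.21. The spread of initial age is not given and is assumed:

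- SD 1 year: 1/2.08 = 48% or 1/2.21 = 45%.
- SD 2 years: 4/5.08 = 79% or 4/5.21 = 77%.
- SD 3 years: 9/10.08 = 89% or 9/10.21 = 88%.

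If RHI depends only on current age, the current-age term is enough. If the covariate is initial age, essentially none of the bias is removed.

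**The case against.** The strongest reply is that no imbalance is shown. The text says the selection is random, and the parenthesis may mean random picks along a date-ordered list. A gap needs a pool clearly above 30 and controls in a different date order, and the documents state neither. This stands, and it is why the point is conditional.

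A reader might infer that sampling is certainly sequential and that follow-up differs by 1.5 to 2.0 years. The documents do not support that. Those figures come from filling all 30 places in the first one or two years (mean 12.13 or 11.63 years, against 10.13 for the whole window). At even entry this needs about 30 × 5 = 150 or 30 × 5/2 = 75 elevated patients who also take part and meet the age and smoking criteria. It also puts the mean follow-up beyond the synopsis's 10 years. If 10 years were a real limit, evaluations would run from August 2008 to December 2010, about 2.4 years. The same calculation then gives gaps of about 1.2 - 0.5 = 0.7 or 1.2 - 1.0 = 0.2 years.

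It can also be said that RHI is protected by age. If current age is matched, RHI is measured at the same age in both groups and only a separate duration effect remains. If initial age is matched, the model's age term carries part of the duration. Both arguments have force, but the second leaves about half or more of a duration effect when initial age has an SD of 1 year or above, and neither reaches the hs-CRP change test.

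**Conclusion.** The concern holds in a limited form. Elapsed time can vary by up to 5 years between patients and enters neither the matching nor any analysis. The selection rule does not exclude a systematic difference between groups. Under date-ordered selection the expected gap is 0 to 1.9 years for assumed pools of 30 to 120.

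The threat is mainly to the unadjusted hs-CRP change comparison, and to a lesser extent to the unadjusted Mann-Whitney test of RHI. The modelled RHI comparison is partly protected. It would go too far to conclude that the primary RHI result is confounded: the documents give no imbalance and no slope of RHI or hs-CRP with time, and the bias figures rest on assumed slopes. The 5 to 10 years in the synopsis and the 2006-2010 window also need to be reconciled.

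**What to change.** - Draw the 30 elevated patients by random number from the full 2006-2010 list, and reword the selection sentence so that it has one meaning.
- State that matching uses values at the initial evaluation and, where feasible, match on date of initial evaluation as well.
- Analyse the hs-CRP change with a model, for example on ranks or on log hs-CRP, that includes years since initial evaluation. Kruskal-Wallis cannot take a covariate.
- Add the same term to the RHI model, and say which age that model uses.
- Report time since initial evaluation by group.
- Reconcile the synopsis interval with the recruitment window.

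The term is still useful after a random draw. With 30 per group spread evenly over the window, the chance gap in mean follow-up has an SD of √(2 × 2.083/30) = 0.37 years.

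The cost is small, because the dates of initial investigation are already used for selection. Some matches will be harder to find, and each model has one more term.

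### The exclusions cover infection and smoking but not known non-infectious inflammatory disease or systemic anti-inflammatory treatment, so the hs-CRP groups can reflect causes other than obesity

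*Combined protocol and SAP*

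**What the plan says.** The synopsis gives the purpose as "To assess whether low grade inflammation in childhood obesity contributes to endothelial dysfunction". It defines exposure by a single cut-off, comparing participants with low grade inflammation "in comparison with those without low grade inflammation (hSCRP < or > 1 mg/L").

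Under Study population, 3. Eligibility criteria, inclusion needs an age of 12–21 years at evaluation, an initial BMI above 1.3 SDS, and "Hs-CRP available at initial evaluation". Nothing is required about why hs-CRP is raised. The exclusions are "Acute or chronic Infection at the time of the study visit" and "Be or have been a smoker of tobacco", and the list ends there.

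Under Study population, 1. Recruitment, "30 participating patients with initially elevated hsCRP will be selected at random". They are then "matched for age, BMI z-score, and blood pressure with the same number of patients without initially elevated hCRP values". The source is children whose metabolic risk was evaluated in 2006–2010, before treatment; the section does not say which treatment is meant.

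Under Study design, 3. Statistical methodology, RHI is compared by a Mann-Whitney test and by a multivariate analysis of variance that takes in current hs-CRP, age, BMI z-score and systolic blood pressure.

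Under Study intervention, 1. Study overview, "During this visit a standard questionnaire on current health status, life style will be filled in". The Privacy policy adds that medical file data are collected and merged with the questionnaire data. No section uses either source to exclude, stratify or adjust.

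**The concern.** hs-CRP stands in for inflammation due to obesity, yet the marker does not tell one cause from another. By excluding infection and smoking, the plan already accepts that competing causes should be removed. Known inflammatory disease of other origin belongs to the same class and is left in.

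The comparison is not randomised. A condition that raises the initial hs-CRP and also lowers the later RHI would confound it, and would do so in the direction of the hypothesis. A positive result could then be read as an effect of inflammation in childhood obesity when part of it comes from another disease. Treatment that lowers hs-CRP could blur the groups in other ways.

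**Working it through.** **Step 1: does any part of the plan close the gap?**

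| Stage | What is used | Covers inflammatory disease or its treatment? |
|---|---|---|
| Inclusion | age, initial BMI, initial hs-CRP available | no |
| Exclusion | infection at the visit, smoking | no |
| Matching | age, BMI z-score, blood pressure | no |
| Adjustment | current hs-CRP, age, BMI z-score, systolic blood pressure | not directly; current hs-CRP may absorb part of a persisting disease |
| Mann-Whitney test | none | no |
| Questionnaire, medical file | collected, no stated use | no |

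**Step 2: what can each condition do?** The groups are formed on the initial hs-CRP, so timing decides the mechanism.

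- Inflammatory disease present at the initial evaluation can raise that hs-CRP and place the child in the elevated group. If it persists, it may also lower RHI at the visit. The bias is then towards the hypothesis.
- Systemic anti-inflammatory treatment at the initial evaluation could lower hs-CRP and place the child in the normal group.
- A disease or drug that starts later cannot change the grouping. It can still affect RHI and current hs-CRP, which matters for the objective that relates RHI to current hs-CRP and for the adjusted analysis.

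**Step 3: how large could the bias be?** From Statistical methodology: mean RHI 1.51, SD 0.2. From Recruitment: 30 per group. Assumed, because the documents give no value: normally distributed RHI, no true effect, k of the 30 elevated-group participants affected, RHI lower by d in those affected, none affected in the comparison group, and a two-sided 5% test (the plan does not state sidedness). The value d = 0.3 is close to the plan's own 20% difference (0.20 × 1.51 = 0.302).

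The shift in group mean is k × d / 30. The Mann-Whitney rejection rates come from simulation with 10,000 replicates (20,000 for the first row).

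| k of 30 | d | Mean shift | Rejection rate |
|---|---|---|---|
| 0 | – | 0 | 4.6% |
| 1 | 0.3 | 0.01 | 4.2% |
| 2 | 0.3 | 0.02 | 5.4% |
| 3 | 0.3 | 0.03 | 6.8% |
| 5 | 0.3 | 0.05 | 10.7% |
| 6 | 0.4 | 0.08 | 17.2% |

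Repeat runs with 20,000 replicates agree within one percentage point, so smaller differences between rows mean nothing. One affected participant is indistinguishable from none.

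**Step 4: the opposite case, dilution.** Suppose a share f of the elevated group has another cause of raised hs-CRP and no effect on RHI. The plan's own figure comes first. With a difference of 0.302 and SD 0.2, the normal approximation gives 2 × (1.96 + 0.84)² × 0.2² / 0.302² ≈ 6.9, so 7 per group and not the stated 27. The stated number fits a 10% difference: 2 × 2.80² × 0.2² / 0.151² ≈ 27.5, so 28, with power 0.79 at 27. That mismatch is a separate matter. For dilution, the mean difference becomes 0.151 × (1 − f), with averaged variance 0.2² + 0.5 × f × (1 − f) × 0.151². Power at 27 per group falls from 0.79 to 0.75 (f = 5%) and 0.69 (f = 10%). With the stated 20% difference it stays at about 0.94 or above up to f = 30%.

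**Step 5: is there room to exclude?** 30 × (1 − 0.10) = 27, so the planned 30 per group still leaves 27 if 10% are removed after enrolment. Screening before selection costs less.

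**The case against.** The best defence is that the problem may be small. The documents give neither a prevalence nor an RHI decrement. Nothing in them suggests that 5 or 6 of 30 non-smoking 12–21-year-olds would have such a disease, and with 1–3 of 30 the false-positive rate hardly moves. There are also partial mitigations: recruitment from an evaluation before treatment, matching on blood pressure, and adjustment for systolic blood pressure and current hs-CRP. That these diseases lower RHI is not stated in the documents either, although the plan's own hypothesis is that raised hs-CRP goes with poorer endothelial function.

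The point about size stands, and it limits the finding. The mitigations do not close the gap. Recruitment before treatment describes 2006–2010 and not the visit, none of the factors is a disease or drug variable, and the Mann-Whitney test adjusts for nothing.

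A reader might infer that diabetes and lipid-lowering, antihypertensive or other vasoactive drugs should be excluded too, because such participants would be counted as having obesity-related inflammation. The documents do not support that. A condition or drug that starts after the initial evaluation cannot change the group, and a drug acting only on RHI does not change it at any time. Background and rationale lists dyslipidemia, insulin resistance and hypertension as accompaniments of obesity, so diabetes and these treatments may lie on the pathway under study. Excluding them at the visit, years after exposure, could select the healthiest participants and distort the comparison.

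**Conclusion.** The gap is real: the plan as written admits participants with known non-infectious inflammatory disease or systemic anti-inflammatory treatment, and nothing later in the plan deals with them. The mechanism that misassigns cause to the elevated group applies to inflammatory disease present at the initial evaluation. Treatment at that time may act the other way, and later conditions affect only RHI and current hs-CRP.

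Under the assumptions above, the false-positive rate is about 4–7% with 1–3 of 30 affected and about 11% with 5 of 30. A reader might take 10–17% as the expected error rate. That needs 17–20% of the elevated group affected (5/30 to 6/30), RHI lower by 0.3–0.4 and an unaffected comparison group, none of which the documents give. The net direction and size of the bias cannot be derived from them. The point supports a cheap improvement to the eligibility rules; it does not show that the study cannot answer its question.

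**What to change.** Add to the exclusion criteria: known chronic inflammatory or autoimmune disease, or systemic anti-inflammatory treatment, at the initial evaluation or at the study visit.

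Check the medical file before selection and matching. The questionnaire cannot serve that purpose, because it is filled in during the single visit; use it there to confirm. If a case comes to light only at the visit, make the primary RHI comparison without that participant and report the full set as a sensitivity analysis.

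Do not exclude diabetes or lipid-lowering and vasoactive drugs by default. Record them and report a sensitivity analysis without those participants.

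The cost is a short amendment, a slightly smaller recruitment pool and slightly narrower generalisability. The documents do not say whether the questionnaire and the file extract record inflammatory diagnoses and medication; if they do not, those items must be added. The planned 30 per group leaves 27 if up to 10% are removed.

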Obesity and overweight have become an important health burden in children and adolescents, with 19% of all children between 5 and 18 years being either obese or overweight in Belgium(1,2). Obesity and especially visceral adiposity early in life may contribute to the development of cardiovascular disease at older age, as it shows tracking into adulthood and is associated with cardiovascular risk

factors such as dyslipidemia, insulin resistance, arterial hypertension and low grade inflammation, in a variable percentage (4) (5)

Low grade inflammation, as assessed by hSCRP, was found to be present in 20.6 % and 19.8 % of overweight children and adolescents (6). In adults, hSCRP levels between 1 and 3 mg/L and above 3 mg/L are considered coronary disease risk factors (7).

Endothelial dysfunction, known to precede the formation of atherosclerotic plaque, can be assessed in a non-invasive manner in children by peripheral artery tonometry. (8) Only few studies have been performed in obese children with this bed-side technique, showing either normal or a disturbed function, reflected by a lower reactive hyperemia index (9, 10,11) The association with low grade inflammation however was assessed in only one study. We hypothesize that in adolescents and young adults with a history of childhood obesity a more disturbed endothelial function will be present in those with and /or current elevated hSCRP value.

Study Objectives

To investigate whether obese and overweight adolescents with an elevated hs-CRP are more at risk for the development of endothelial dysfunction assessed peripheral artery tonometry, compared to those with a normal hs-CRP at their initial evaluation for obesity-associated metabolic syndrome

To assess the degree of endothelial dysfunction, assessed by the reactive hyperemia index by peripheral artery tonometry in adolescents and young adults with a history of childhood obesity in relation to their current hs CRP value

To investigate the changes in hs-CRP and adiposity in adolescence and young adulthood of initially obese children and adolescents with either normal or elevated hs-CRP levels

Study outcomes

1. Primary outcome

Reactive hyperemia index (RHI) measured by the EndoPAT device

2. Secondary outcome

hs CRP value , BMI z-score and body fat percentage assessed by skinfold thickness

Study design

1. Overall design

This is an observational cohort study

2. Randomization/blinding procedure.

Not applicable.

3. Statistical methodology

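### The infection exclusion covers only the day of the visit, so a participant who has just recovered can be sampled once with a transiently raised current hs-CRP and counted as having low grade inflammation

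*Combined protocol and SAP*

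**What the plan says.** The only infection rule is in Study population, 3. Eligibility criteria, which excludes "Acute or chronic Infection at the time of the study visit". No section gives an interval before the visit, a repeat sample, an hs-CRP value above which a sample is set aside, or a rule for rescheduling.

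Under Study intervention, 1. Study overview, "A single visit is planned", and the blood for hs-CRP is drawn then. The same paragraph states: "During this visit a standard questionnaire on current health status, life style will be filled in". The questionnaire is not reproduced, and no action is attached to its answers.

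The visit value is used in three ways:

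- **Second objective:** RHI is studied "in adolescents and young adults with a history of childhood obesity in relation to their current hs CRP value".
- **Third objective and secondary outcome:** the visit value is the end point of the change in hs-CRP.
- **RHI model (Statistical methodology):** the group difference is analysed "taking current hCRP, age, BMI z-score, and systolic blood pressure into account".

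The synopsis sets the cut-off for low grade inflammation at 1 mg/L ("hSCRP < or > 1 mg/L"). The first objective forms the main groups from the initial value: those with an elevated hs-CRP are "compared to those with a normal hs-CRP at their initial evaluation for obesity-associated metabolic syndrome".

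**The concern.** The study uses hs-CRP as a marker of chronic low grade inflammation, but hs-CRP also rises with acute infection. The exclusion shows that the authors want to keep acute-phase values out. However, it looks at the visit day only, and the marker can stay raised after symptoms have gone. With one sample and a cut-off as low as 1 mg/L, nothing in the data would later separate a fading acute response from a settled raised value.

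The protocol does set a pre-visit window for tonometry (no strenuous sport in the preceding 24 hours). It sets none for hs-CRP.

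Three results are at stake. The relation between RHI and current hs-CRP would be diluted. The hs-CRP change score would gain spurious increases. Adjustment of RHI for current hs-CRP would be less complete than intended.

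**Working it through.** The plan gives no figure on this point to reproduce. From the documents come the 60 participants (Recruitment), one sample each, and the 1 mg/L cut-off (synopsis). Everything else below is an assumption, shown as a range.

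**1. Time to fall to 1 mg/L.** Assume hs-CRP halves every 19-24 h once the stimulus ends, from a peak of 10-50 mg/L. Days = log2(peak / 1) × half-life / 24.

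| Peak | Half-lives | At 19 h | At 24 h |
|---|---|---|---|
| 10 mg/L | 3.32 | 2.6 days | 3.3 days |
| 50 mg/L | 5.64 | 4.5 days | 5.6 days |

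**2. Share of visits affected.** Assume 2-4 minor infections a year, each leaving 3-6 raised days after symptoms end. Share = infections × days / 365.

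- Low: 2 × 3 / 365 = 1.6%; × 60 = 1.0 visit.
- High: 4 × 6 / 365 = 6.6%; × 60 = 3.9 visits.

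**3. Participants who change category.** Only those whose settled value is below 1 mg/L can be reclassified. Let π be the share truly above the cut-off at the visit. It is unknown, so take 20% (close to the prevalence quoted in the Background) and 50% (the planned split on initial hs-CRP). Number = 60 × (1 − π) × share.

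- π = 20%: 48 × 1.6% to 48 × 6.6% = 0.8 to 3.2.
- π = 50%: 30 × 1.6% to 30 × 6.6% = 0.5 to 2.0.

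**4. Effect on the RHI contrast if current hs-CRP is split at 1 mg/L.** Let q be the share from step 2, applied to those truly below. If a recent infection does not itself alter RHI, the observed contrast keeps the fraction π / [π + (1 − π)q] of its true size.

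| π | q = 1.6% | q = 6.6% |
|---|---|---|
| 20% | 0.94 | 0.79 |
| 50% | 0.98 | 0.94 |

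**5. Effect if current hs-CRP enters as an untransformed continuous value.** The plan states no transformation. Assume settled values are log-normal with median 1 mg/L and log-SD s of 0.8 or 1.0. Their variance is (e^(s²) − 1)e^(s²) = 1.70 or 4.67. One participant in 60 carrying an extra 10 mg/L adds 100 × (1/60) × (59/60) = 1.64. The fitted slope then keeps about 1.70 / 3.34 = 0.51 or 4.67 / 6.31 = 0.74 of its size. With an extra 5 mg/L the added variance is 0.41, and the slope keeps 1.70 / 2.11 = 0.81 or 4.67 / 5.08 = 0.92.

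**The case against.** **The size rests on assumptions.** Apart from the 60 visits and the cut-off, no input is in the documents. A minor infection need not leave hs-CRP above 1 mg/L for 3-6 days, and a raised value in a recovered participant is possible, not certain. This stands, and it is why the result is given as a range.

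**The reach is limited.** The change in hs-CRP is to be analysed by a rank test, which restrains a few extreme values. The unadjusted Mann-Whitney comparison of RHI uses groups defined by initial hs-CRP. Both points stand. The synopsis does not say which hs-CRP its cut-off refers to, so a reader might infer that the main groups are misclassified too. The Study Objectives and the Recruitment section form them from the initial value, so that inference fails.

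**The questionnaire may already ask about recent infection.** It is not reproduced, so this is possible. But no consequence is attached to an answer, and the criterion would still admit the participant.

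**A stronger reading is tempting.** A reader might infer that a passing cold on the day removes a participant for good and depletes the matched pairs. The documents do not support this:

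- The criterion depends on status at the visit, and the text neither provides for nor forbids rescheduling or replacement.
- Controls are matched after the participants with elevated initial hs-CRP have been selected, so another control can be sought.
- The planned tests are unpaired, so losing one member of a pair does not remove the other. At an assumed 5%-10% infected on the day, with no replacement, the expected number per group is 30 × 0.95 = 28.5 to 30 × 0.90 = 27.0, against the stated 27.
- The stated 27 is itself not a firm threshold. A 20% difference on 1.51 is 0.302, and with SD 0.2 the two-sided normal formula gives 2 × [0.2 × (1.960 + 0.842) / 0.302]² = 6.9, or 7 per group. That mismatch is a separate matter.

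**Conclusion.** The concern holds for the missing look-back interval. Applied as written, the rule admits transient acute-phase values into a single measurement read against 1 mg/L.

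Under the stated assumptions about 1 to 4 of 60 visits are affected, and about 0.5 to 3.2 participants change category. The RHI contrast by current hs-CRP would keep 79% to 98% of its size if dichotomised. An untransformed continuous analysis could lose more from one large value. The expected direction is towards missing a real association.

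The effect is confined to the current-hs-CRP objective, the hs-CRP change analysis and the covariate adjustment of RHI. The groups defined by initial hs-CRP are untouched, and no claim of permanent loss or depleted pairs is made. This is a modest weakness, worth correcting because the correction is cheap and an unrecorded recent infection cannot be reliably identified afterwards from one sample.

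**What to change.** - Reword the criterion to cover acute infection or fever at, or within a fixed interval before, the study visit. Fourteen days is one example and exceeds the assumed 2.6-5.6 days to reach 1 mg/L; the investigators should set the length.
- State that the visit is then postponed until the interval has passed, and that chronic infection remains an exclusion.
- Ask about recent infection when the appointment is confirmed and again in the planned health questionnaire, and record the answer.

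The cost is one reworded criterion, one question asked twice, and a few rescheduled visits. As a protocol change it goes to the Ethics Committee, as the protocol already requires. The planned sample size does not change.
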